Our group recently found that microRNA which are highly enriched in skeletal muscle (i.e., myomiR) are sensitive to differing exercise modes with or without essential amino acid plus carbohydrate supplementation (unpublished data). In this investigation we found that weighted endurance-type exercise diminished miR-1-3p, miR-206, miR-208a-5p, and miR-499 expression, while conventional cycle ergometry endurance exercise increased microRNA expression. However, when cycle ergometry was combined with ingestion of essential amino acids plus carbohydrate, microRNA expression was either downregulated or remained the same immediately post and during the recovery phase, compared to baseline values. Divergent microRNA were all identified to target insulin signaling, with miR-206, miR-208-5p, and miR-499 were all predicted to target Akt, an intermediate signaling protein between IRS1 and AS160. These findings suggest that diminished microRNA expression immediately following exercise may have a functional role in mediating glucose uptake to replenish glycogen stores. Corroborating our findings, previous investigations have reported the microRNA acutely altered by exercise. Following an acute bout of endurance exercise there is diminished expression of miR-23, while mRNA expression of PGC-1 α and its downstream targets are upregulated (23, 24). When miR-23 is overexpressed in skeletal muscle there is a reduction in total PGC-1 α mRNA and protein content that results in reduced efficiency of mitochondrial function, an organelle crucial to cellular energy production (23). Furthermore, endurance exercise also downregulates miR-494, another inhibitor of PGC-1 α , allowing for increased gene expression of PGC-1 α and mitochondrial transcription factor A (25). While interventions have been conducted examining the relationship of microRNA expression to energy sensing genes in response to endurance exercise, no study has investigated the influence of altered glycogen availability in response to dietary manipulation on microRNA expression. Understanding how glycogen availability alters expression of microRNA will enable determination of their functional role in regulating carbohydrate metabolism to support energy availability to fuel physical performance.

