Following identification of skeletal muscle microRNA that had a significant change, Taqman® probes (Applied Biosystems) will be used to assess the expression of these microRNA in serum to determine their potential use as noninvasive markers of altered carbohydrate metabolism following glycogen depletion and repletion. Total circulating miRNA will be extracted from 200 μ L serum using miRNeasy Serum/Plasma kit, which allows for extraction and purification of small (< 200 nt) cell-free RNA (Qiagen, Valencia, CA, USA). Exosomal circulating miRNA will also be extract from 1000 μ L serum using miRCURY™ RNA Isolation Kit to measure miRNA. To avoid introduction of potentially contaminating material, prior to RNA extraction serum samples will be centrifuged for 10 min at 4°C to remove cellular debris. Supernatant will be removed and transferred to a new tube without disturbing the pellet. Due to the small amount of RNA in the serum, 3.5 μ L of a Spike-In Control (C. elegans miR-39; Qiagen) will be added to all samples prior to extraction of RNA to determine the yield of template recovered. After extraction 3 μ L of serum RNA will be reverse transcribed using the TaqMan® microRNA RT kit (Applied Biosystems) with miRNA-specific stem-loop RT primers pooled in 1X-Tris-EDTA (TE) buffer for a final dilution of 0.05X. A pre-amplification step will be performed after reverse transcription to increase cDNA template using a primer pool of 20 X Taqman® Small RNA Assays (Applied Biosystems) for miRNA of interest at 0.05X concentration in 1X TE buffer. All serum miRNA will be normalized to the geometric of external (Spike-In Control C. elegans miR-39) and internal controls to allow for both technical and inter-individual normalization (47). Geometric mean of controls will be used to correct for possible outlying values and abundance differences between the different controls (48).

All reverse transcription for mRNA and miRNA, and pre-amplification of serum miRNA will be conducted in a T100™ Thermal Cycler (Bio-Rad, Hercules, CA). A StepOnePlus™ real-time PCR system (Applied Biosystems) will be used to perform all mRNA and miRNA analysis. Fold changes will be calculated using the $\Delta\Delta C_T$ method as described below in statistical analysis section.

Bioinformatics Analysis

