32 Hard copy data records will be stored for a minimum of three years from the time the study is completed.
33 Electronic data records will be maintained for a period of at least five years after the study has been
34 completed.
35

36 **B5.6 Managing Data and/or Human Biological Specimens for Future Research**

37 Any use of the samples outside of this defined protocol will be submitted as a protocol amendment or a
38 new protocol. Samples will be retained for future analyses once the protocol is closed if the subject
39 provided permission in the informed consent document.
40

41 **B5.8 Statistical Analysis**

42 **B5.8.1 Sample Size Estimation**

43 Statistical power and sample size were determined using the minimum fold change required for a
44 physiologically relevant difference in microRNA expression. Variance (standard deviation) was based
45 on recent publications assessing change in microRNA expression in skeletal muscle (18, 50, 51) and
46 circulating (34, 35, 52) in response to an acute bout of exercise. Using this information the sample
47 size necessary to determine statistical significance between intervention arms, with a mean fold
48

1 change of 1.5 ± 1 is 9 per group, with an alpha of 0.05 and 80% power. In the present study, 12
2 volunteers will be studied in a repeated measures crossover design to account for potential greater
3 inter-individual variability.
4

5 **B5.8.2 Data analysis**

7 Statistical analyses will be conducted using either SPSS (IBM Corp. Armonk, NY), SAS 9.3 (SAS
8 Institute Inc., Carey, NC), or equivalent. Common descriptive statistics will be used to describe
9 volunteer characteristics. Shapiro-Wilk tests will be used to determine normality of data. Mixed
10 model repeated measures ANOVA will be performed to determine main effects of time (baseline,
11 immediately, 3-hr, and 24-hr post glycogen depletion), carbohydrate intake ($6.0 \text{ g} \cdot \text{kg}^{-1} \cdot \text{d}^{-1}$ versus $1.5 \text{ g} \cdot \text{kg}^{-1} \cdot \text{d}^{-1}$) and time-by-carbohydrate interactions for skeletal muscle and circulating microRNA, mRNA
12 expression, and markers of nutritional status. If interactions are significant, Bonferroni correction will
13 be used to examine these relationships. Correlation coefficients and multiple regression analysis will
14 be used to evaluate relationships between study outcome measures. The alpha level will be adjusted

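### The plan does not say on what scale PCR expression is modelled; if untransformed delta-delta-CT fold changes go into the ANOVA, the time effect is tested less well than on the log scale

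*Combined protocol and SAP*

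**What the plan says.** In B5.4, under mRNA and microRNA Expression, the plan states: "Fold changes will be calculated using the" delta-delta-CT method, with the description deferred to the statistical section. The same paragraph says that a "real-time PCR system (Applied Biosystems) will be used to perform all mRNA and miRNA analysis". In practice PCR covers muscle mRNA and serum microRNA; muscle microRNA is screened by sequencing read counts, described earlier in that subsection.

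The promised description is not in B5.8. B5.8.2 says a mixed "model repeated measures ANOVA will be performed to determine main effects of time (baseline", followed by "immediately, 3-hr, and 24-hr post glycogen depletion), carbohydrate intake" and the time-by-carbohydrate interaction. It applies this to skeletal muscle and circulating microRNA, mRNA and nutritional markers. Baseline is therefore one of four time levels. On distribution it says only "Shapiro-Wilk tests will be used to determine normality of data" and attaches no consequence to the result.

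B5.8.1 is the one place that shows a scale, giving the required sample size for a mean fold "change of 1.5 ± 1 is 9 per group, with an alpha of 0.05 and 80% power".

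**The concern.** A fold change is a ratio of two noisy quantities. If each value is divided by the same volunteer's baseline and the ratios are modelled untransformed, two things happen. Baseline becomes exactly 1 for everyone, with no variance, and its measurement error moves into every later time point. And the mean of the later ratios exceeds 1 even when expression has not changed, so the test of equal means over time is not a test of no change. The scale is also lopsided: a 1.5-fold rise is +0.50 and a 1.5-fold fall is 1/1.5 − 1 = −0.33.

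The time effect matters here. The first objective in B4 covers depletion as well as repletion, and both visits are identical until the beverage is given. Depletion can therefore be tested only as a change over time. B5.4 also sends microRNAs with significant changes to pathway analysis, so wrong calls can carry forward.

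**Working it through.** **The plan's own figure.** A two-sample, two-sided t-test with difference 1.5, SD 1 and alpha 0.05 has power 79.7% at 8 per group and 84.8% at 9. The stated 9 per group is reproduced, but only by taking 1.5 as a distance from zero. A ratio's no-change value is 1.

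**Spread (assumption).** Reading 1.5 ± 1 as a log-normal ratio:
- log SD = √ln(1 + (1/1.5)²) = √ln(1.444) = 0.606, which is 0.606/0.693 = 0.875 on the log2 scale;
- mean ratio to own baseline with no change = exp(0.606²/2) = 1.20.

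With an SD of 0.5 instead of 1, the log SD is √ln(1 + (0.5/1.5)²) = 0.325 and the mean ratio is exp(0.325²/2) = 1.054.

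**Simulation.** 12 volunteers, 2 visits, 4 times, normal errors of equal variance on the log scale, 40,000 trials per setting. Unless noted, the time F-test uses the subject-by-time error. The Greenhouse-Geisser figures come from separate runs at the same spread.

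Own-baseline calibrator, log2 SD 0.875:

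| Quantity | Ratio | Log |
|---|---|---|
| Type I error, time F-test, uncorrected | 13.3% | 4.9% |
| Type I error, random-intercept model | 7.0% | about 2% |
| Any false increase vs baseline (Bonferroni) | 10.6% | 1.0% |
| Any false decrease vs baseline (Bonferroni) | 0.0% | 1.1% |
| Power, sustained 1.5-fold decrease | 45% | 90% |
| Power, sustained 1.5-fold increase | 97% | 90% |

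With Greenhouse-Geisser correction, type I error on ratios is 8.5%, and power for the sustained decrease is 39% on ratios against 87% on logs. In the random-intercept model, even log ratios to own baseline miss the 5% level (about 2%), because baseline is still fixed without variance. This is a reason to keep the measured baseline in the model.

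Sensitivity to the assumed spread, own-baseline calibrator, uncorrected F-test:

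| log2 SD (log SD) | Mean ratio, no change | Type I error, ratio | Power for decrease, ratio vs log |
|---|---|---|---|
| 0.5 (0.35) | 1.06 | 8.5% | 99.9% vs 100% |
| 0.875 (0.61) | 1.20 | 13.3% | 45% vs 90% |
| 1.25 (0.87) | 1.46 | 17.5% | 8% vs 59% |

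**Group-mean calibrator, log2 SD 0.875.** Type I error is 4.3%, with false increases and decreases about equal (2.4% and 1.9%). Power on ratios is about 85% for a sustained 1.5-fold decrease and about 76% for an increase, against 90% on logs. These two figures also depend on how much volunteers differ from one another, which cancels under the other approaches.

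**Carbohydrate tests, own-baseline ratios, no true effect.** Interaction type I error is 4.8%, 4.2% and 3.7% at the three spreads. The arm effect is symmetric, 2.2% each way at log2 SD 0.875. Neither is inflated.

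**The case against.** The strongest reply is that the plan never says ratios are what is tested. Delta-delta-CT is itself a log2 difference, so computing fold changes does not mean modelling them, and a baseline listed as a time level fits an analysis of four measured values at least as well as a baseline fixed at 1. Nor does the sample-size figure settle the scale, since it reproduces only against a null of zero. This stands. It makes the finding conditional, but nothing in the text excludes the weaker analysis.

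Second, the comparison that B5.8.1 powers is between arms, and those tests are not inflated. That also stands; what remains exposed is the time main effect.

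Third, one could hope that Shapiro-Wilk would catch the skew. On a single cell of 12 values it does so about 39 to 40% of the time at the larger spread. Applied to two-way residuals it does so about 74% of the time, and to all 12 × 2 × 3 = 72 post-baseline values pooled, over 99%. So it would be wrong to say that the test would usually miss the skew. The gap is that nothing follows from the result.

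A reader might also infer from B2 that the expected changes are decreases, the direction ratios detect worst, because it says "These findings suggest that diminished microRNA expression immediately following exercise may have a functional role in mediating glucose uptake to replenish glycogen stores". The section does not support that for this trial. It reports that several muscle-enriched microRNAs rose with conventional cycle ergometry, the mode used here, and fell with weighted exercise. With cycling plus amino acids and carbohydrate they fell or were unchanged. Decreases are also cited for miR-23 and miR-494. The expected directions are mixed.

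**Conclusion.** The concern holds in conditional form. The cross-reference leads nowhere, the analysis scale and calibrator are unstated, and the natural reading is worse than the log scale for the time effect under either calibrator at the spread implied by 1.5 ± 1. With own-baseline ratios, type I error is about 7 to 13% depending on the model, and power for a sustained 1.5-fold decrease is about 39 to 46% against 87 to 90%. With a group-mean calibrator only power is lost, in both directions. At a log SD near 0.33 power is almost untouched and the excess of false positives is modest.

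A reader might infer that the plan as written over-calls increases and hides decreases throughout. The documents do not support that: the directional bias needs an own-baseline calibrator they never state, does not inflate the arm or time-by-carbohydrate tests, and does not reach the muscle microRNA sequencing screen, to which delta-delta-CT does not apply.

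The sizes rest on log-normal errors, equal error variance at all times, and the assumed spread. The change should be made, because the unstated choice moves the error rates materially and settling it in advance is free.

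**What to change.** In B5.8.2, state that:
- all PCR outcomes (muscle mRNA, serum microRNA, and any muscle microRNA measured by PCR) are modelled as normalised delta-CT values, that is, on the log2 scale;
- the measured baseline is kept as a level of time, and values are not divided by the volunteer's own baseline before modelling;
- time and carbohydrate contrasts are taken on the log2 scale, with estimates and confidence limits back-transformed to geometric mean fold changes for reporting only;
- this choice does not depend on the Shapiro-Wilk result.

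Correct the forward reference in B5.4 so that it points to this text. The cost is a few sentences, with no new data, samples or volunteers. Reported fold changes become geometric rather than arithmetic means, which agrees with the geometric averaging that B5.4 already uses for the serum controls.

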12 subtracting exogenous glucose oxidation from total CHO oxidation. The first 40 min of steady-state
13 exercise will allow for equilibration between the $^{13}C/^{12}C$ in expired CO_2 and the $^{13}C/^{12}C$ in CO_2 produced in
14 tissues (45). Thus, endogenous glucose oxidation will only be calculated from samples obtained in the last
15 40 min of steady-state exercise (40 to 80 min).

16

17 *Muscle Glycogen*

18 Approximately 20 mg of muscle will be dehydrated in a freeze dryer. Samples will then be ground to
19 powder and visible connective tissue will be removed. Powdered muscle will be placed in 500 μ l 2 N HCl.
20 Samples will then be placed in an incubator for 120 min at 100 °C. Following incubation samples will be
21 neutralized with 1500 μ l 0.67 N NaOH. Muscle glycogen will be in solution at this point. Glycogen will be
22 quantified by a fluorometric assay (Sigma-Aldrich, St. Louis, MO, USA).

23

24 *Intramuscular Triglyceride Concentrations*

25 Intramuscular triglyceride concentrations will be determined using the Folch method (46). Dehydrate
26 muscle will be homogenized in a 2:1 chloroform-to-methanol solvent. Following extraction, samples will be
27 saponified in ethanolic KOH at 60 °C, and glycerol content will be determined using a commercially available
28 colorimetric assay (Sigma)

29

30 *mRNA and microRNA Expression*

31 Total RNA will be isolated from approximately 25 mg of muscle using a mirVana™ miRNA isolation kit
32 (Invitrogen, Carlsbad, CA, USA). Quantity and quality of RNA will be assessed using a Nanodrop ND-
33 1000spectrophotometer (Nanodrop, Wilmington, DE, USA). Equal amounts of total RNA will be
34 synthesized into cDNA for analysis of mRNA (iScript™ Advanced cDNA Synthesis Kit; Bio-Rad) and a
35 TaqMan® microRNA RT kit (Applied Biosystems, Foster City, CA, USA). Individual primers will be used to
36 determine the mRNA expression of known intracellular targets regulating muscle metabolism, to include
37 but not limited to PGC-1 α , SIRT1, ACC, AMPK, PDK4, IRS1, and GLUT4. miRNA (20-40 bp) will be size-
38 selected from total RNA using Illumina's protocol (US Army Center for Environmental Health Research,
39 Frederick, MD). The sorted miRNA will be tagged and assayed using the Illumina NextSeq instrument.
40 Briefly, 500 ng total RNA will be used to construct sequencing libraries. Subsequently, the samples will be

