41 amplified using index-tagged primers to facilitate multiplexing. The amplified cDNA constructs will be size-
42 selected, quality controlled before loading to the NextSeq instrument to generate 50 base reads. Image
43 analysis and base calling will be performed using the Illumina pipeline.

44

45 Preprocessing of raw base calls, sample de-multiplexing, trimming and filtering will be similar to that
46 described in 'Analysis of sequencing output'. For the miRNA quantification/enrichment, reads are first
47 aligned to the Rfam RNA database to filter and profile other small RNA species in the samples. Then reads
48 are mapped for small RNA annotation against reference zebrafish mature mature RNA sequences from the
49 miRBASE database. The miRNA read count matrix for each sample will be generated using open source
50 tools such as PICARD.

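### The analysis scale and calibrator for qPCR fold changes are not defined; if linear fold changes to each volunteer's own baseline are modelled, the time test is too liberal and falls can be harder to detect

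*Combined protocol and SAP*

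**What the plan says.** The last paragraph of the mRNA and microRNA Expression text in B5.4 states: "Fold changes will be calculated using the" delta-delta-CT "method as described below in statistical analysis section". B5.8 contains no such description. It does not say whether the modelled value is the linear ratio or its logarithm, and it does not say what each sample is compared with.

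Three statements in B5.8 bear on how the values would be used:

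- **B5.8.1** sizes the trial on a mean fold "change of 1.5 ± 1 is 9 per group, with an alpha of 0.05 and 80% power". This is the only place where an outcome scale carries numbers.
- **B5.8.2** plans a mixed "model repeated measures ANOVA will be performed to determine main effects of time (baseline" and three later times), carbohydrate intake and their interaction, for muscle and circulating microRNA and for mRNA. It names no covariance structure and no sphericity correction.
- **B5.8.2** also says "Shapiro-Wilk tests will be used to determine normality of data". It states no transformation or alternative analysis if normality fails.

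On platform, B5.4 says of muscle microRNA: "The sorted miRNA will be tagged and assayed using the Illumina NextSeq instrument". Later it says that a "real-time PCR system (Applied Biosystems) will be used to perform all mRNA and miRNA analysis". Serum microRNA and mRNA are clearly qPCR outcomes. Whether muscle microRNA is also measured by qPCR is left open.

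**The concern.** A fold change to a volunteer's own baseline equals exactly 1 at baseline for everyone. Afterwards it is a ratio, right-skewed, with a mean above 1 even when nothing has changed. If such values enter an ANOVA that has baseline as a time level, a constant column is compared with three skewed columns that share a denominator. The time test can then reject because of the scale alone. A 1.5-fold rise (+0.5) and a 1.5-fold fall (−0.33) are also unequal distances from 1, although biologically they are the same size.

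The time effect addresses the depletion part of Objective 1, and serum microRNA is central to the second part of that objective. Section B2 gives weight to falls: it reports lower expression of several microRNAs after exercise and proposes that such falls help glucose uptake. A scale that is weak for falls would be a poor choice here.

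**Working it through.** **Plan's own figure.** A two-sided two-sample t-test with difference 1.5 and SD 1 gives 79.65% power at n = 8 and 84.8% at n = 9, so 9 per group reproduces. (Two-sided is an assumption.) It reproduces only if 1.5 is taken as the difference between arms.

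**Is 1.5 ± 1 a linear-scale statement?** A normal variable with mean 1.5 and SD 1 is negative with probability Φ(−1.5) = 6.7%, which is impossible for a fold change. If the figures describe fold changes, a skewed distribution is needed.

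**Log-scale SD (assumption).** Take a log-normal fold change with mean 1.5 and SD 1:
- σ(ln) = √ln(1 + (1/1.5)²) = √ln 1.444 = 0.606
- σ(log2) = 0.606 / ln 2 = 0.875

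**Unchanged target, own-period baseline.** Fold change = 2^−(ΔCT at t − ΔCT at baseline). At baseline this is 2⁰ = 1, with variance 0. Afterwards its mean is exp(0.606²/2) = 1.20.

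**Simulation.** 20,000 trials per setting: 12 volunteers, 2 conditions, 4 times, independent normal errors on the log2 scale, nominal 5% test of time. The Monte Carlo error near 13% is √(0.13 × 0.87/20,000) = 0.24 points. A 1.5-fold change is log2 1.5 = 0.585.

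Own-period baseline, log2 SD 0.875; sustained means the change is present at all three later times:

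| Analysis of time | Type I error, linear | Type I error, log2 | Sustained fall, power linear / log2 | Sustained rise, power linear / log2 |
|---|---|---|---|---|
| RM-ANOVA, uncorrected | 13.2% | 4.9% | 46% / 91% | 97% / 90% |
| Greenhouse-Geisser | 8.5% | 3.5% | 39% / 88% | 93% / 87% |
| Compound-symmetry mixed model | 6.7% | 2.2% | 38% / 85% | 94% / 85% |
| Multivariate | 6.9% | 5.0% | 54% / 79% | 85% / 78% |

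A separate run of the uncorrected analysis gave 13.5% against 5.1% for type I error, and 45% against 90% for the sustained fall.

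**Sensitivity to the SD** (linear, own-period, uncorrected). Type I error is 6.5%, 8.3%, 11.1%, 14.8% and 16.8% at log2 SD 0.3, 0.5, 0.7, 1.0 and 1.2. At SD 0.5, power for the sustained 1.5-fold fall is 99.9%.

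**Sensitivity to the effect** (SD 0.875, uncorrected). A 1.5-fold fall at one later time only has 74% power linear against 90% log2. A sustained two-fold fall has 98% against 100%.

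**Sensitivity to the calibrator** (linear, SD 0.875, uncorrected):
- One own baseline used for both periods: type I error 5.6%.
- Group-mean baseline: type I error 4.5% to 5.0% across two runs. All four time means, baseline included, are about 1.15, so nothing appears to rise. Power is 86% to 89% for a sustained fall and 78% for a rise.

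**Other tests.** With the own-period baseline, the carbohydrate and time-by-carbohydrate tests each reject 4.4% under the null.

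**The case against.** The strongest reply is that nothing in the plan says linear values are modelled. B5.4 says only that fold changes are calculated, and B5.8.2 names expression as the outcome. Listing baseline as a time level fits delta-CT at four times at least as well as a column fixed at 1. This stands: linear modelling is an inference from the sample-size input, and an own-baseline calibrator is an assumption.

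It also stands that 13% is one corner of the range. It needs an own-period calibrator, a log2 SD near 0.875 and no sphericity correction, all together. That SD treats 1.5 as the mean of a fold change, whereas the 9 per group reproduces only with 1.5 as the difference. The SD is therefore an assumption rather than a planning value of the protocol.

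A reader might infer that the skew also distorts which muscle microRNAs are taken to serum assay. The documents do not support this. That selection is described as following from sequencing, and delta-delta-CT does not apply to read counts. Nor can one conclude that raw counts are analysed. B5.4 says "The miRNA read count matrix for each sample will be generated using open source" tools, and it refers preprocessing to a description that is not in the text available.

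What the reply does not remove is the empty cross-reference. The Shapiro-Wilk test does not fill the gap, because no action follows from it. The text as written permits the unfavourable analysis as well as the sound one.

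**Conclusion.** The point holds as a conditional one about qPCR outcomes: serum microRNA, mRNA and any muscle microRNA measured by qPCR. The promised description is missing, and the choice it leaves open matters.

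Under linear fold changes to own-period baseline, with log2 SD 0.875 and 12 volunteers, unchanged targets average 1.20. The time test then rejects about 7% to 13% of the time instead of 5%, and power for a sustained 1.5-fold fall is roughly halved in the uncorrected analysis. The inflation is smaller at lower SDs, and the power loss is gone at SD 0.5. Both largely vanish with a group-mean calibrator.

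Three stronger readings are not supported: that the plan commits to linear analysis, that the error is 13% whatever the implementation, and that falls are always under-detected. With a group-mean calibrator, falls are not the weaker direction. The comparison between arms, for which the sample size was set, is not shown to be inflated. The change is still worth making, because the log2 analysis held its error at or below about 5% in every model tried, with nearly equal power for rises and falls.

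**What to change.** In B5.8.2, supply the description that B5.4 promises:

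- qPCR outcomes are modelled as delta-CT (log2 scale) at every time point, including baseline, with the reference controls named for muscle and serum.
- Contrasts are back-transformed as 2^−contrast and reported as fold changes with 95% CIs. Fold change is used for display only.
- The covariance structure or sphericity correction is stated.
- Normality is checked on this scale, and the action that follows from the check is stated.

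Use delta-CT itself rather than delta-delta-CT to own baseline, so that baseline keeps its variance. In the compound-symmetry model above, power for the sustained fall is 92% when all values are shifted only by a common constant (equivalent to delta-CT), against 85% when each is referred to its own baseline.

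The cost is SAP wording only. Samples, assays, number of volunteers and software are unchanged, and results can still be reported as fold changes.
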